10.2.1.1 COVID-19 related considerations

To assess the impact of COVID-19 mass vaccination on TEAEs, a sensitivity analysis will present all TEAEs excluding TEAEs assessed as exclusively related to COVID-19 vaccine by the investigator. TEAEs recorded as related to both study medication and COVID-19 vaccination should not be excluded. A complementary table and listing of TEAEs related to COVID-19 vaccine will be presented.

Another sensitivity analysis will present all TEAEs excluding TEAEs with start date on or up to 5 days after date of COVID-19 vaccine. Note that study participants may receive more than one administration of COVID-19 vaccine. A complementary table and listing of TEAEs with start date on or up to 5 days after date of COVID-19 vaccine will also be presented.

10.2.2 AE summaries

The following summaries will be provided by treatment group for the Initial Treatment Period, and the Initial and Maintenance Treatment Period combined based on the SS, and AMS respectively. In addition, all summaries of TEAEs based on “100 subject years” will include EAIR (with 95% confidence interval) and EAER. For AEs that emerged after 112 days but still within the 140 days window, those AEs would be classified as TEAE. These AEs will be excluded from the outputs based on the Initial Period but included in the AE summaries for Initial and Maintenance Treatment Period.

- Incidence of TEAEs – Overview
- Incidence of TEAEs per 100 subject years by SOC, HLT, and PT
- Incidence of Serious TEAEs per 100 subject years by SOC, HLT, and PT
- Incidence of TEAEs Leading to Study Participant Discontinuation per 100 subject years by SOC, HLT, and PT
- Incidence of TEAEs Leading to Death by SOC, HLT, and PT
- Incidence of TEAEs by Maximum Relationship by SOC, HLT, and PT
- Incidence of Serious TEAEs by Relationship SOC, HLT, and PT – Note: For EudraCT reporting purposes
- Incidence of Related Serious TEAE by SOC, HLT, and PT
- Incidence of Severe TEAE per 100 subject years by SOC, HLT, and PT

- Incidence of TEAEs Leading to Death by Relationship by SOC, HLT, and PT – Note: For EudraCT reporting purposes
- Incidence of TEAEs by Maximum Severity, SOC, HLT, and PT
- Incidence of TEAEs by decreasing frequency of PT
- Incidence of TEAEs Above Reporting Threshold of 5% by SOC and PT
- Incidence of Non-Serious TEAEs by SOC, HLT, and PT
- Incidence of Non-Serious TEAEs by Maximum Relationship SOC, HLT, and PT
- Incidence of Non-Serious TEAEs Above Reporting Threshold of 5% by SOC and PT
- Incidence of Non-Serious TEAEs Above Reporting Threshold of 5% by Relationship SOC and PT
- Incidence of Related TEAEs per 100 subject years by SOC, HLT, and PT
- Incidence of Related TEAEs Above Reporting Threshold of 5% by SOC and PT
- Incidence of TEAEs – Suspected and Confirmed COVID-19 cases by SOC, HLT and PT
- Incidence of TEAEs Excluding TEAEs Exclusively Related to COVID-19 Vaccine by SOC, HLT, and PT
- Incidence of TEAEs Exclusively Related to COVID-19 Vaccine by SOC, HLT, and PT
- Incidence of COVID-19 Vaccine Interval Censored TEAEs by SOC, HLT, and PT
- Incidence of COVID-19 Vaccine Interval TEAEs by SOC, HLT, and PT

Suspected and confirmed COVID-19 cases will be identified with the preferred terms “Corona virus infection” or “Corona virus test positive”.

The following subset of tables will also be presented for the Maintenance Treatment Period using the MS:

- Incidence of TEAEs – Overview
- Incidence of TEAEs per 100 subject years by SOC, HLT, and PT
- Incidence of Serious TEAEs per 100 subject years by SOC, HLT, and PT
- Incidence of TEAEs Leading to Discontinuation per 100 subject years by SOC, HLT, and PT
- Incidence of TEAEs Leading to Death by SOC, HLT, and PT

The following tables will be presented for the Initial Treatment Period:

- Incidence of TEAEs Above Reporting Threshold of 5% with Risk Differences by SOC and PT
- Incidence of Serious TEAEs and Risk Differences by SOC and PT

The following table will be presented for the combined Initial and Maintenance Treatment Period. This summary will include only AEs that occur while a participant is on bimekizumab.

Any AEs in the Initial Treatment Period that begin while a participant is on placebo will be excluded.

- Incidence of TEAEs per 100 subject years by SOC, HLT, and PT and by Time of Onset Relative to Anti-bimekizumab Antibody Status. This will include columns for the following:
 - TEAEs starting before the first ADAb positive result (includes ADAb categories 2 and 5) where TEAEs have occurred before the following events: a) the first positive ADAb result for subjects in category 2 and b) the first post-Baseline boosted ADAb titer result for subjects with titer results and the first post-Baseline positive ADAb result for subjects with positive ADAb at Baseline with no other samples with titer available for subjects in category 5
 - TEAEs starting on the same date or after the first ADAb positive result (includes ADAb Categories 2, 3, 4, 5 and 6) where TEAEs have occurred on or after the following events: a) the first positive ADAb results for subjects in categories 2, 3, 4 and 6, and b) the first post-Baseline boosted ADAb titer result for subjects with titer results and the first post-Baseline positive ADAb result for subjects with positive ADAb at Baseline with no other samples with titer available for subjects in category 5
 - TEAEs for subjects who are ADAb negative at all timepoints (includes ADAb Category 1)

The tables with risk differences will also be accompanied by figures (dot plots) which show the incidence of the adverse events and corresponding 95% risk difference confidence intervals. These will be ordered by descending order of risk difference (bimekizumab vs placebo).

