3.3 Definition of Baseline values

Section 8.3.3 details the derivation of the Baseline value for the HSSDD assessment. For all other assessments, the below applies.

A Baseline value for a participant is defined as the latest non-missing measurement for that participant up to and including the day of administration of first study medication, unless otherwise stated. If a Baseline assessment is taken on the same day as first administration of study medication, it is eligible to be used as the Baseline value, even in the case that the time of the assessment is recorded as taking place after the time of first study medication administration. This is considered acceptable as this measurement is still the best representation of the Baseline value of the given assessment since it is highly unlikely that the study medication could have an impact on any measurement in such a short period of time. However, such cases should be rare as study center personnel are instructed to do all assessments at the Baseline visit prior to administering study medication. One exception to this rule is plasma concentration of bimekizumab. If Baseline plasma concentration is measured at a time after the first administration of study medication, then it will not be eligible to be considered as a Baseline plasma concentration. Such cases will be discussed with the quantitative clinical pharmacologist.

For randomized participants for whom no start date of treatment is available, the Baseline value will be considered as the last available value on or before the randomization date.

If a Baseline measurement is missing or not collected, and a Screening value is available, the Screening value will be utilized as Baseline instead.

Baseline values for component scores should be computed using components from the same visit where the relevant measurements were recorded prior to dosing. For example, if the Screening visit has all of the components, but the Baseline visit is missing 1 or more components, the Baseline value for the component score should be calculated using the Screening visit values.

When the time of first dose is derived, it will be based on the first injection of study treatment, regardless of whether or not it is an active treatment.

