- The prevalence of immunogenicity, separated by treatment group, and defined subcategory, will be reported by visit, defined as (cumulative) proportion of participants having confirmed positive ADA_b samples at any visit up to and including that visit. Missing samples will not be included in the denominator.
- The time to achieving treatment-emergent ADA_b positivity, separated by treatment group and defined subcategory, will be analyzed based on Kaplan-Meier methods. This will be shown only for Categories 2 and 8 above. Participants will be considered to have an event at the time point at which treatment emergent ADA_b positive is first achieved (taking the MSR into consideration for sub-category 5). Participants classified as treatment-emergent ADA_b negative will be censored at the time of the last available ADA_b result.
- A summary of HiSCR₅₀ responders at Week 16, separated by treatment group, as a function of ADA_b titer will be presented graphically.
- Individual plots of plasma bimekizumab concentrations/ ADA_b titer both plotted on the Y-axes by visit (x-axis) for the full treatment period (excluding SFU for interim analyses and

including SFU for final analyses) will be presented for participants with and without HiSCR₅₀ response at Week 16.

- Spaghetti plots of ADAb titer (y-axis) by visit (x-axis), separated by treatment group for all ADAb positive participants, including Baseline positive participants.
- Box plots of ADAb titer (logscale) by time to first ADAb positivity by treatment group.

The groups for defining ADAb status for safety subgroup analyses are as follows:

- AEs starting before first ADAb positive result
- AEs starting on or after first ADAb positive result
- AEs for participants who were always ADAb negative

This is further explained in Section 10.2.2.

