10.2.1 Data considerations

Treatment-emergent AEs are defined as those AEs that have a start date on or following the first dose of study treatment through the final dose of study treatment + 140 days (covering the 20-week SFU period). If it is not possible (due to partial dates) to determine whether or not an AE is treatment-emergent then it will be assumed to be a TEAE.

An AE will be assigned to the Initial Treatment Period if it started between the first administration of IMP on Day 1 up to Week 16. An AE will be assigned to the Maintenance Treatment Period if it started between the Week 16 study drug administration and Week 48.

If an AE occurs on the date of a treatment switch, the event is attributed to the original treatment. The only exception to this is if the AE fulfills any of the criteria specified below:

- Events that fulfill the anaphylaxis criteria for acute events (refer to Appendix A in Section 12.1)
- Hypersensitivity events identified by the SMQ “Hypersensitivity (SMQ)” (see Section 12.1 Appendix A)
- Events with an high level term (HLT) of “Administration site reactions NEC”
- Events with an HLT of “Injection site reactions”

The rules for imputing partial start or stop dates are outlined in Section 4.2.4.

Any TEAEs that occur during the SFU Period will be attributed to the period in which the participant was before initiating the SFU Period.

Duration of AEs will not be calculated if there is missing stop date information.

If the intensity of an AE is unknown, it is considered as severe. If the relationship to study drug is missing, it is considered as related. Note that if the seriousness of an adverse event is unknown, every attempt should be made to resolve this prior to a snapshot for an interim analysis or database lock; in the exceptional case that the seriousness of an adverse event is still missing then no imputation should be applied for this characteristic.

Adverse events will be presented as “number of participants (percentage of participants) [number of events]”. In this style of output, “[number of events]” will include all cases of an AE including repeat occurrences in individual participants, while “number of participants” will count each participant only once.

Subject time at risk represents the time a participant is at risk for having an AE. The definitions for subject time at risk (in days) are outlined in Section 10.1. These definitions will be used for exposure-adjusted AE summaries.

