Selected AE summaries will include the exposure-adjusted incident rate (EAIR) with associated 95% CI and the exposure adjusted event rate (EAER).

The EAIR is defined as the number of participants (n) with a specific AE adjusted for the exposure and will be scaled to 100 subject-years:

$$EAIR = 100 \times n / \sum_{i=1}^N (T_{Exp(i)})$$

Where $T_{Exp(i)}$ is the exposure time and N is the number of participants at risk.

If a participant has multiple events, the time of exposure is calculated to the first occurrence of the AE being considered. If a participant has no events, the total time at risk is used.

Exact Poisson 95% confidence intervals for incidence rates are calculated using the relationship between the Poisson and the Chi-square distribution (Ulm, 1990; Fay and Feuer, 1997):

$$LCL = \chi^2_{2n,\alpha/2} / 2$$

$$UCL = \chi^2_{2(n+1),1-\alpha/2} / 2$$

where n is the number of participants with a specific AE for the incidence rate of interest and is the basis for the number of the degrees of freedom for the chi-square quantile for the upper tail probability χ^2 .

The EAER will be the number of AEs including repeat occurrences in individual participants divided by the total time at risk scaled to 100 patient-years and calculated using:

$$EAER = 100 \times N_{AE} / \sum_{i=1}^N (T_{Risk(i)})$$

where N_{AE} is the total number of AEs, T_{Risk} is the time at risk for each participant, and N is the total number of participants at risk.

No confidence interval will be computed for EAER.

Selected summaries, as specified in Section 10.2.2, will include the risk difference between bimekizumab and placebo. The risk difference is calculated as:

$$RD = IP_{BKZ} - IP_{PBO}$$

where IP_{BKZ} is the incidence proportion for the bimekizumab-treated group and IP_{PBO} is the incidence proportion for the placebo group. Note that incidence proportion simply refers to the percentage of participants within the specified treatment group that experienced a given adverse event.

The standard error for the risk difference is calculated as follows:

$$SE_{RD} = \sqrt{\left(IP_{BKZ} \times \left(\frac{1 - IP_{BKZ}}{n_{BKZ}} \right) \right) + \left(IP_{PBO} \times \left(\frac{1 - IP_{PBO}}{n_{PBO}} \right) \right)}$$

where n_{BKZ} is the number of participants in the bimekizumab-treated group and n_{PBO} is the number of participants in the placebo group.

The corresponding confidence interval for the risk difference is as follows:

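### The TEAE table by antibody onset restricts and splits the events but not the person-time, so rates are too low for converters and the placebo/bimekizumab arm; Section 9.3.2 also names Category 8 where 7 fits

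*SAP*

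**What the plan says.** **Events.** SAP Section 10.2.2 specifies, for the combined Initial and Maintenance Treatment Period, "Incidence of TEAEs per 100 subject years by SOC, HLT, and PT and by Time of Onset Relative to Anti-bimekizumab Antibody Status". It restricts the numerator twice: "This summary will include only AEs that occur while a participant is on bimekizumab", and "Any AEs in the Initial Treatment Period that begin while a participant is on placebo will be excluded". There are three columns:

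- *Before* the first positive result: Categories 2 and 5 only.
- *On or after* it, where "TEAEs have occurred on or after the following events": Categories 2, 3, 4, 5 and 6.
- Always negative: Category 1.

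For Category 5 the split falls at the first boosted titer or, where no titer is available, at the first positive result after Baseline. As a per-100-subject-years table it carries both the EAIR and the EAER.

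**Person-time.** Section 10.2.1 refers to the time-at-risk definitions in Section 10.1 and says "These definitions will be used for exposure-adjusted AE summaries". The EAER divides by total time at risk. The EAIR stops at the first occurrence for participants with an event; otherwise "If a participant has no events, the total time at risk is used". For the combined period, Section 10.1.3.2 counts from the date of first dose. Section 3.3 says of the time of first dose that "it will be based on the first injection of study treatment, regardless of whether or not it is an active treatment".

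**Time to antibody positivity.** Section 9.3.2 plans a Kaplan-Meier analysis of time to treatment-emergent positivity and adds: "This will be shown only for Categories 2 and 8 above". The same section defines Category 8 as positivity at Baseline (3, 4, 5 and 6 combined) and Category 7 as total treatment-emergent positivity (2 and 5 combined).

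**The concern.** A rate is interpretable only if its person-time is the time in which a counted event could have happened. Here the events are confined to a window (on bimekizumab, on one side of conversion), while the default denominator is the whole follow-up. The rates come out too low, and by unequal amounts across columns and arms.

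This is the planned table that asks whether adverse events are more frequent once antibodies appear. A plan followed to the letter would tend to make antibody-positive participants look safer than always-negative ones, and the placebo/bimekizumab arm look safer than the arms on bimekizumab from Week 0.

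The Category 8 reference is a separate matter. It puts a Baseline-positivity group into an analysis of treatment-emergent events and leaves out the pooled treatment-emergent group.

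**Working it through.** The SAP states no rate or event count for this table, so there is no figure to reproduce. The check compares the days in which an event can count with the days the default rule puts in the denominator.

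**Inputs**

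- Placebo period: 16 × 7 = 112 days (Section 10.1.1.2 gives the same figure).
- Total time at risk, Week 48 completer entering the extension (Section 10.1.3.2, final visit − first dose + 1): 48 × 7 + 1 = 337 days.
- Total time at risk with full safety follow-up (last dose − first dose + 141; last dose at Week 46 per Section 7): 46 × 7 + 141 = 463 days.
- Antibody sampling after Baseline: Weeks 4, 8, 12, 16, 20, 24, 36 and 48 (Section 9.3.2). Conversion times are not given; those below are assumptions.

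**EAER.** With an unchanged event count, displayed rate ÷ true rate = eligible days ÷ total time at risk.

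*Placebo/bimekizumab arm, all columns together*

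- Extension completer: (337 − 112)/337 = 225/337 = 0.668, so 33% too low.
- With safety follow-up: (463 − 112)/463 = 351/463 = 0.758, so 24% too low. This takes follow-up events within the 140-day window as countable.

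*Category 2 or 5 participant on bimekizumab throughout, 337 days*

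| Assumed first positive or boosted result | *Before* | *On or after* |
|---|---|---|
| Week 8 | 56/337 = 0.166 | 281/337 = 0.834 |
| Week 16 | 112/337 = 0.332 | 225/337 = 0.668 |
| Week 24 | 168/337 = 0.499 | 169/337 = 0.501 |
| Week 36 | 252/337 = 0.748 | 85/337 = 0.252 |

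The two fractions sum to 1 because the same 337 days are used twice. With a constant true rate, the displayed *after*-to-*before* ratio would be 0.668/0.332 = 2.0 for conversion at Week 16 and 0.252/0.748 = 0.34 at Week 36. That contrast reflects when people convert, not risk.

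*Converter in the placebo/bimekizumab arm.* Both losses apply. For conversion at study Week 24: *before* (168 − 112)/337 = 0.166; *on or after* 169/337 = 0.501.

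**EAIR.** Assume a constant hazard λ in an eligible window of length L that starts a days after first dose, with total time T. Let X be the time from the start of the window to the event.

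- Probability of an event: p = 1 − exp(−λL).
- Matched denominator: p/λ.
- As-written denominator: a·p + E[X; X < L] + (1 − p)·T, where E[X; X < L] = p/λ − L·exp(−λL).

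For the placebo/bimekizumab extension completer (a = 112, L = 225, T = 337), true rates of 5, 20 and 100 per 100 subject-years display as 3.3, 13.1 and 60.0 (ratios 0.66, 0.65 and 0.60). First-event censoring does not remove the deflation.

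**Who is not affected.** Categories 3, 4 and 6 are positive at Baseline and enter only *on or after*. In arms on bimekizumab throughout, all their time belongs there. Category 1 in those arms also has matching events and person-time.

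**Section 9.3.2.** Within Category 8 only Category 5 can have a treatment-emergent event. The adjoining clause on the minimum significant ratio for sub-category 5 fits Category 7.

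**The case against.** The strongest reply is that the SAP never writes a denominator for this table. Section 10.1.3.2 says only date of first dose, and the sentence that counts a placebo injection as first dose stands in the section on Baseline values. Section 3.2.1 gives the placebo/bimekizumab arm a second origin at first bimekizumab dose, so the authors knew it needed one. On that view the plan is silent rather than wrong, and a programmer would split the time. It is true that the mismatch is reached through the general rule. But that rule is stated to cover exposure-adjusted AE summaries, nothing overrides it here, and the Section 3.2.1 origin is for relative day only.

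The table is also descriptive, and the participant counts, percentages and event counts shown with the rates are unaffected. That stands, and it limits the severity.

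Three stronger readings are tempting but unsupported:

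- A reader might infer that every antibody-positive participant is counted in both columns. Only Categories 2 and 5 are, so the *on or after* column is diluted in proportion to their share, which is unknown in advance. The percentages in the table above describe one converter, not the column.
- A reader might infer a flat one-third understatement in the placebo/bimekizumab arm. That holds for extension completers; with safety follow-up it is about 24%.
- A reader might infer that no treatment-emergent antibody curve would be produced. Category 2 is itself treatment-emergent and is shown. Only the pooled Category 7 curve is lost.

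**Conclusion.** The point holds in this form. Followed as written, the plan gives rates that are too low for Category 2 and 5 participants in both columns they enter, and for every column of the placebo/bimekizumab arm. The direction is certain because the numerator is fixed and the denominator is too large.

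The size rests on assumptions: 24% to 33% for the event rate in the placebo/bimekizumab arm, depending on whether participants have safety follow-up or enter the extension; and, for a converter with 337 days, 17% to 75% of the true rate *before* and 83% to 25% *on or after* as assumed conversion moves from Week 8 to Week 36. Because the always-negative column in the bimekizumab-randomized arms is not deflated, the comparison favours antibody-positive participants.

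This is a safety-table error worth correcting. It does not touch the efficacy inference. The Category 8 reference is a smaller, separate wording error.

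**What to change.** In Section 10.2.2, state the person-time for this table:

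- Start time at risk at the first bimekizumab dose in every arm.
- For Categories 2 and 5, end *before* time on the day preceding the first positive (or first boosted) result and start *on or after* time on that day.
- Leave Categories 3, 4 and 6 wholly in *on or after*, and Category 1 wholly in the always-negative column.
- For the EAIR, apply first-event censoring within each column; for the EAER, divide by that column's person-time.

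In Section 9.3.2, replace Category 8 with Category 7 in the time-to-positivity analysis, so that the total treatment-emergent curve is produced in addition to the Category 2 curve.

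The cost is a few lines of SAP text and one split person-time dataset. No new data are needed.
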